#### 7.8.2 Adverse events

All Adverse events during the course of the study will be coded using the medical dictionary of regulatory activities (MedDRA) current at the start of the study and summarised by treatment group. AEs will be summarised by treatment, primary system organ class (SOC), preferred term (PT), relationship assessment and severity.

All solicited AEs identified via separate phone calls for the US will also be entered in the general AE section of the eCRF. Therefore, no separate analysis will be conducted.

The SOCs as well as the PTs within each summary table will be sorted by frequency in the total column in decreasing order.

AEs will be reported separately as pre-treatment or screening period AEs (any AE occurring prior to the first injection of study medication) and treatment emergent AEs (any AEs after first injection of study medication).

In general, all adverse events will be listed by treatment group, subject number, and period. For AE onset and end dates, the study day relative to the first injection will be listed.

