#### 7.8.2.1 Definitions related to adverse events

Pre-Treatment adverse event: Any AE with date and time of onset prior to the first injection of study medication. Pre-treatment AEs might also be termed Screening Period AEs.

Treatment emergent AE (TEAE): Any AE with date and time of onset after first injection of study medication. In case of (partially) missing date or time that could indicate a TEAE, it will be analysed as treatment emergent.

TEAEs during the treatment period: Any AE with date and time of onset after first injection of study medication and up to and including date of last injection of study medication + 28 days.

Adverse Drug Reactions (ADRs): Any AE that is possibly, probably or definitely related to study medication or the assessment of the relationship to study medication is missing as reported in the eCRF.

Adverse events related to study procedure: Any AE that was documented with causal relationship to a study procedure of "yes" in the eCRF.

Adverse events of special interest (AESI): Any AE that was documented as "AESI confirmed by Adjudication Committee" in the eCRF.

Local AE: Any AE that is documented with the category "Local (injection site) adverse event" in the eCRF.

Systemic AE: Any AE that is documented with the category "Systemic adverse event" in the eCRF.

Other AE: Any AE that is documented with the category "Other adverse event" in the eCRF, i.e. any adverse event that is neither local nor systemic.

AEs leading to premature discontinuation of treatment: Any AE for which action taken is documented as "Permanent discontinuation of the IMP" in the eCRF.

AEs leading to temporary discontinuation of treatment: Any AE for which action taken is documented as "Temporary discontinuation of the IMP" in the eCRF.

AEs leading to premature discontinuation of study: for which action taken is documented as "Withdrawal from the Study" in the eCRF.

Duration of adverse event (expressed in [days]) is calculated as follows:

- End date/time of AE onset date/time of AE
- In case of missing onset time or missing end time: end date of AE onset date of AE +
- In case of (partially) missing onset date or (partially) missing end date no calculation will be done

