## 7.8.2.2 Overview summary tables for adverse events

An overview summary of the following AE types will be provided, presenting number and percentage of subjects experiencing at least one AE of the respective AE type in each treatment group as well as the corresponding number of events.

- Any AE
- Any ADR
- Any severe AE
- Any severe ADR
- Any AE of special interest
- Any serious AE
- Any serious ADR
- Any non-serious AE
- Any AE leading to premature discontinuation from treatment
- Any AE leading to temporary discontinuation from treatment
- Any ADR leading to premature discontinuation from treatment
- Any ADR leading to temporary discontinuation from treatment
- Any AE leading to premature discontinuation of study
- Any ADR leading to premature discontinuation of study
- Any local TEAE
- Any systemic TEAE
- Any other TEAE, not classified as local or systemic AE

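### The ADR definition and most overview rows are not limited to treatment-emergent events, so a pre-injection event with missing causality can be counted as a drug reaction

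*SAP*

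**What the plan says.** SAP 7.8.2.1 (Definitions related to adverse events) sorts events by onset. A pre-treatment event is "Any AE with date and time of onset prior to the first injection of study medication", and a TEAE is "Any AE with date and time of onset after first injection of study medication". The ADR definition that follows depends on causality alone: "Any AE that is possibly, probably or definitely related to study medication or the assessment of the relationship to study medication is missing".

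The opening text of SAP 7.8.2 (Adverse events) sets a general rule: "AEs will be reported separately as pre-treatment or screening period AEs", with treatment-emergent AEs as the other category.

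Two lists of outputs follow:

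- The SOC/PT summary tables (the later heading that also carries the number 7.8.2) limit some rows to treatment-emergent events. The rows for ADRs, serious ADRs and local, systemic and other AEs carry no such limit.
- The overview table (7.8.2.2) is described as "presenting number and percentage of subjects experiencing at least one AE of the respective AE type in each treatment group", with event counts added and no period given. Its rows for AEs, ADRs, severe, serious and non-serious events, AESIs and discontinuations are unrestricted. Only the last three rows are limited, beginning with "Any local TEAE".

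**The concern.** A reaction to a drug cannot begin before the drug is given, so one would expect the ADR definition to start from TEAEs. It starts from all AEs instead, and it treats a blank relationship as related. Either choice alone would do little harm. Together they let a screening event with an empty causality field meet the definition.

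The table lists do not remove the problem. The overview table puts rows that cover every recorded AE beside rows that cover only TEAEs, so its lines do not share one set of events. In the SOC/PT tables a subject could be an ADR case for a preferred term without being a TEAE case for it.

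Frequency, severity and relationship of AEs to treatment is one of the five safety endpoints in SAP Table 1. What is at stake is the absolute ADR rate in each arm, and whether two programmers working from this text would produce the same table.

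**Working it through.** The documents give no figure on this point, so the check is mainly a comparison of text, followed by a short calculation of scale.

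**Step 1. Can pre-injection events be in the safety data?** Yes. The protocol's schedule of activities marks AEs at Visit 1 and first drug administration at Visit 2. The Safety Set (SAP Table 3) holds subjects with at least one injection. Screen failures drop out, but the screening events of treated subjects remain.

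**Step 2. Which of them can meet the ADR definition?**

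| Pre-injection event in a treated subject | Meets the ADR definition as written? |
|---|---|
| Relationship rated not related | No |
| Relationship missing | Yes |
| Relationship rated possible, probable or definite (implausible before dosing) | Yes |

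**Step 3. Do the row labels exclude them?**

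| Category | SOC/PT tables | Overview table (7.8.2.2) |
|---|---|---|
| All events | TEAE | any AE |
| ADR, serious ADR | no limit | no limit |
| Serious events | treatment-emergent in the first list; all SAEs in the severity/relationship list | no limit |
| AESI | treatment-emergent | no limit |
| Leading to discontinuation, by AE type | TEAE; ADR rows without limit | no limit |
| Local, systemic, other | no limit | TEAE |

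The labels differ between the two lists for all events, AESIs, discontinuations and local/systemic/other events. For SAEs they also differ within the SOC/PT section. Neither list has a row or table for pre-treatment events, so the separate reporting promised in the opening of 7.8.2 has no listed output.

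**Step 4. Scale.** Inputs: N=555 randomised in Year 1 (protocol, number of subjects planned) and 1:1 allocation (protocol, overall design). Assumption: the Safety Set is close to that number.

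- Subjects per arm: 555 / 2 = 277.5.
- Each subject who is an ADR case only because of a pre-injection event adds 1 / 277.5 = 0.36 percentage points to that arm's rate.
- For an assumed 0, 1, 5 or 10 such subjects per arm, the rate rises by 0, 0.36, 1.8 or 3.6 points (5 / 277.5 = 1.8%; 10 / 277.5 = 3.6%).

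**Step 5. Effect on the contrast between arms.** Pre-injection events cannot depend on the treatment later received, so the same share *q* of subjects is expected in each arm. If such events are also independent of later ADRs, a true rate *p* becomes *p* + (1 − *p*)*q*. A difference *D* between arms then becomes *D*(1 − *q*). With *q* = 10 / 277.5 = 3.6%, the difference keeps 96.4% of its size.

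**The case against.** The strongest reply is that the opening of 7.8.2 governs everything below it. If pre-treatment and treatment-emergent events are reported separately, the ADR rows belong to the treatment-emergent report. The SOC/PT list supports this: it pairs TEAE rows with ADR rows throughout, as if ADRs were the related part of the TEAEs. SAP section 6 also requires eCRF data to be checked and relevant queries answered before analysis, and a blank causality field is an obvious query. The listings show period and study day, so an early event stays identifiable.

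Much of this stands. A reader might infer that pre-injection events *will* be reported as drug reactions. The documents do not show that, because the separate-reporting rule points the other way and no table shells are available. A reader might also suppose that causality is the field most likely to be blank at screening, or that the comparison with placebo will be seriously diluted. The first has no source in the documents. The second would need a high rate of unresolved blanks, and the planned AE tables give only counts and percentages, with no ratio or test. The unrestricted any-AE row mixes periods but does not turn an event into a drug reaction.

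The reply does not settle the text, however. The general rule is not carried into any listed output. The overview table limits three rows to TEAEs and leaves the rest open, which suggests that the open rows are meant to be open. The pairing in the SOC/PT list hints that ADRs are a subset of TEAEs, but no definition says so.

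**Conclusion.** The point holds as a defect of definition and labelling. Followed literally, the ADR rule can count a pre-injection event with missing causality, or one implausibly rated related, as a drug reaction, and the overview table combines all-AE rows with TEAE rows. Both conflict with the separate-reporting rule in 7.8.2. Certain misreporting is not established.

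The number of affected subjects is not in the documents and is probably small once queries are resolved. The figure of 0.36 points per subject rests on a Safety Set of about 555 split equally, and the range of 0 to 10 subjects per arm is an assumption. The expected effect is similar in both arms, so absolute ADR rates would move more than the difference between them when ADRs are uncommon. The missing-counts-as-related rule is a normal conservative choice; the difficulty comes only from combining it with no limit on onset. The correction is worth making because it removes an inconsistency in a stated safety endpoint at almost no cost.

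**What to change.** 1. In SAP 7.8.2.1, define an ADR as *any TEAE rated possibly, probably or definitely related to study medication, or with no relationship recorded*. The existing rule that an event with an incomplete onset date or time is treated as a TEAE where that is possible then carries over to ADRs.
2. In the SOC/PT list and in 7.8.2.2, label every row as treatment-emergent, including the local, systemic, other, serious, AESI and discontinuation rows and the SAE entry in the severity/relationship list.
3. Add one line or one short table for pre-treatment AEs, so that the separate reporting already required by 7.8.2 has an output.

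The cost is SAP wording and matching table titles. No new data, design change or additional analysis is needed, and it should be done before the safety tables are programmed.

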## 7.8.2 Summary tables for analysis of adverse events

The number and percentage of subjects with

- TEAEs
- ADRs
- treatment emergent serious adverse events (SAEs)
- serious ADRs
- treatment emergent adverse events of special interest (AESIs)
- TEAEs leading to premature discontinuation of treatment
- ADRs leading to premature discontinuation of treatment
- TEAEs leading to temporary discontinuation of treatment
- ADRs leading to temporary discontinuation of treatment
- TEAEs leading to premature discontinuation of study

- ADRs leading to premature discontinuation of study
- local AEs
- systemic AEs
- other AEs, not classified as local or systemic AEs

will be summarised by treatment group, MedDRA SOC and PT.

For the analysis of the severity and the relationship of AEs, the worst severity and the strongest relationship per subject and type of AE will be used. The number and percentage of subjects with at least one AE by MedDRA SOC, PT and severity/relationship will be displayed only for

- all TEAEs
- all ADRs

all serious adverse events (SAEs).

## 7.8.2.2 Overview summary tables for adverse events

An overview summary of the following AE types will be provided, presenting number and percentage of subjects experiencing at least one AE of the respective AE type in each treatment group as well as the corresponding number of events.

- Any AE
- Any ADR
- Any severe AE
- Any severe ADR
- Any AE of special interest
- Any serious AE
- Any serious ADR
- Any non-serious AE
- Any AE leading to premature discontinuation from treatment
- Any AE leading to temporary discontinuation from treatment
- Any ADR leading to premature discontinuation from treatment
- Any ADR leading to temporary discontinuation from treatment
- Any AE leading to premature discontinuation of study
- Any ADR leading to premature discontinuation of study
- Any local TEAE
- Any systemic TEAE
- Any other TEAE, not classified as local or systemic AE

## 7.8.3 Safety laboratory

Serum Chemistry	Glucose, Sodium, Uric acid, Urea, Potassium, Calcium, Creatinine, Chloride, Total protein, Phosphorus, Cholesterol, Albumin, Total Bilirubin, Alkaline phosphatase, LDH, AST, ALT, GGT, CRP
Haematology	Haemoglobin, haematocrit, total WBC and differentials, total RBC, RBC indices, and platelet count.
Urinalysis (using a urine dip-stick)	pH, Protein, Glucose, Ketones, Bilirubin, Blood, Nitrite, Urobilinogen, Leukocytes.

Abbreviations: ALT = alanine aminotransferase; AST = aspartate aminotransferase; CRP = C-reactive protein; GGT = gamma-glutamyl transferase; LDH = lactate dehydrogenase; RBC = red blood cells; WBC = white blood cells.

Summary tables will be created for serum chemistry and haematology.

For urinalysis, a frequency table will be created summarizing the overall sample.

#### 7.8.4 Vital signs

Vital signs (systolic and diastolic blood pressure, pulse rate, respiratory rate, and body temperature) will be measured in a semi-supine position after 5 minutes rest for the subject in a quiet setting without distractions using a completely automated device.

Vital signs (systolic and diastolic blood pressure, pulse rate, respiratory rate, and body temperature) will be measured after the subject has been in the supine position for at least 5 minutes at Visit 2 and Visit 7.

Summary statistics will be created per vital sign parameter and visit/timepoint (pre- and post-injection) for all scheduled treatment visits by treatment group including the absolute values per visit/timepoint and the absolute change from baseline.

#### 7.8.5 Physical examination

A complete physical examination includes assessment of the following: general appearance, skin, head, neck, eyes, ears, nose, throat, lymph nodes, abdomen, musculoskeletal, cardiovascular, respiratory and neurological systems. Rectal, breast, pelvic, gynaecological, and/or urogenital examinations will not be performed. Complete physical examination will be performed at Visit 1 and Visit 11, or at the early termination visit if applicable.

An assessment of the subjects' mental status to determine their ability to participate in the clinical trial will be included at the Visit 1 physical examination assessment only.

#### 7.8.6 Other safety data

Urine pregnancy tests will only be performed on female subjects of childbearing potential. on every visit (except safety follow-up calls). If positive, a serum pregnancy test should be done.

The corresponding results will only be listed by subject.

## 8 SOFTWARE AND STATISTICAL PROGRAMMING

The statistical analysis will be performed using the SAS® statistical software package in Version 9.4 or higher.

